**Appendix 7**  
**International Centre for Diarrhoeal Disease Research, Bangladesh**  
**Fish intervention on vitamin A status in children – a study in Mirpur**

**Perception of Mola Form**

1. Study ID#
2. Child Mapping ID#
3. Household mapping ID#
4. Camp \_\_\_\_\_ Camp code
5. Date of interview     - 2002
6. Respondent 1= Mother    2=Father  
3= Other (relation to child) \_\_\_\_\_
- 

**Introduction:**

All children were given a fish curry during the study. The fish curry was made either with mola or with rui. Your child was given the mola curry every day during the study. We will like to ask you and your child who took part in the study some questions regarding mola and the mola curry.

---

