### Specific objectives

- To assess the efficacy of vitamin rich small fish, mola in improving vitamin A status (based on serum retinol concentrations, results from the Relative Dose Response (RDR) method, serum retinol binding protein and prealbumin concentrations). This will be done by comparing the increase in vitamin A status after supplementation of mola fish with the increase in vitamin A status after supplementation of non/low vitamin A rich big fish, rui and supplementation of rui with added retinyl palmitate, in a daily meal for 9 weeks to marginally vitamin A deficient children (3-7 y) in a Dhaka slum.
- To investigate the impact of intake of vitamin A rich small fish on iron status (based on haemoglobin, serum ferritin and serum transferrin receptor) in children in comparison with that of non/low vitamin A rich big fish and non/low vitamin A rich big fish with added retinyl palmitate.
- To investigate whether the factors: a) nutrient intake during study (based on repeated 24 h recall interview), b) initial vitamin A and iron status, c) changes in iron status, d) markers of infection (based on C-reactive protein (CRP) and  $\alpha$ -1 anti-chymotrypsin (ACT)), e) morbidity during study (based on incidence of infection such as diarrhoea, acute respiratory infections, fever, measles and night blindness), f) marker of protein energy malnutrition (based on prealbumin), g) initial and/or change in nutritional status (based on height, weight, MUAC) affect the change in vitamin A status after intake of vitamin A rich small fish in comparison with that of intake of non/low vitamin A rich big fish and non/low vitamin A rich big fish with added retinyl palmitate. In addition, if an effect is seen it will be investigated whether some subgroups benefit more than others from the intervention.
- To investigate qualitatively the mothers' perceptions of the effect of the mola supplementation on the general well being of the children as well as the acceptance of mola for habitual use among the children and their families.

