#### ***Mothers' perceptions of the effect of the mola supplementation***

At *endpoint* a qualitative questionnaire (Appendix 7: Perception of mola form) will be conducted (in the mola fish group) to evaluate the effect of the mola supplementation on the general well being of the children as well as the acceptance of the proposed mola meal for habitual use among the children and their families.

The mothers will be asked how the children felt after eating the test meal, how well they like the test meals and what benefits they think the test meal have on the nutritional status of their children. The mothers will also be asked if they will prepare the mola test meal at home and which resources they need to do so as well as which constraints they may face and how they can overcome these constraints.

This data from this questionnaire are important for large scale implementation of the results of this study, taking into account factors such as socio-economic status of the household and specific constraints for consuming mola.

Both structured and open ended questionnaire will be used to assess the perception of the mothers about mola fish. A focus group discussion with 15 mothers at 3-4 sessions will be conducted to assess the perception.

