#### **Calculation of sample size**

Using retinol rich foods, fruit or vegetable, de Pee *et al* (1998a) found an increase in serum retinol of 0.23  $\mu\text{mol/L}$ , 0.12  $\mu\text{mol/L}$ , 0.07  $\mu\text{mol/L}$  respectively from a baseline of approximately 0.70  $\mu\text{mol/L}$  in a 9 weeks' intervention study in children 7-11 y. A dose of 650 RE/d given in two meals daily was used. The maximum standard deviation, 0.17  $\mu\text{mol/L}$  in the change in serum retinol from baseline to the end of the study was found in the fruit group.

The expected increase in serum retinol in the mola group in this study, 0.15  $\mu\text{mol/L}$  is based on an expected increase which is lower than that found in the group given the retinol rich food but higher than that in the group given fruit. Children in the positive control group might show a similar or a larger increase in serum retinol concentration than the mola group.

Assuming similar prevalence and distribution of serum retinol concentration at baseline in Bangladeshis as in the Indonesian children, about 0.70  $\mu\text{mol/L}$  and the expected increase amounts to a 20% increase from the baseline value.

The number of participants in each group,  $n$  is calculated from power calculations based on the following formula (Armitage & Berry, 1987):

$$n = [(Z_{\alpha} + Z_{\beta})^2 * (sd_1^2 + sd_2^2)] / d^2$$

$$Z_{\alpha} = 1.96 \text{ for } \alpha = 0.05, \quad Z_{\beta} = 1.28 \text{ for } \beta = 0.10 \text{ (power of 0.90)}$$

$sd_1, sd_2$  = standard deviation of the change in serum retinol from baseline to the end of the study for group 1 and group 2  $sd_1 = sd_2 = 0.20 \mu\text{mol/L}$

$d$  = difference in change in serum retinol between group 1 and group 2,  $d = 0.15 \mu\text{mol/L}$

The sample size required in each group is 37. Assuming a maximum possible drop out of 40%, the total number of children in each intervention group is calculated to be approximately 60. The total number of children to be used in this study is 180.

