### Test meal preparation and distribution

The test meals will be prepared at a centrally located building in the Mirpur slum. The building, which will be rented for 6 months, will be used to conduct the health examination of the children, blood drawing, food storage and cleaning, cooking and feeding of test meals to 180 children. Four head cooks, 24 local kitchen helpers and 7 research assistants will be in charge of preparing and distributing the meals.

The head cooks will be in charge of cooking all dishes, while the local kitchen helpers are needed, especially for the peeling, cleaning and cutting of the vegetables. On a daily basis, four dishes (rice, mola fish curry, rui fish curry and vegetable curry) will be prepared; approximately 130 kg boiled rice, 70 kg vegetable curry, 10 kg mola curry and 15 kg rui curry. In addition, the local kitchen helpers will help in bringing the children to the building, make the children feel welcome, prepare them for eating (for example seeing that they wash their hands), arrange them in intervention groups, and in preparation for receiving the different test meals. They will also assist with meal distribution, encourage and motivate the children to eat the test meal, especially all of the fish curry. In order to ensure that the children eat all the fish curry served, they will first be served the fish curry along with the rice and after finishing the fish curry, they will be served the vegetable curry. The test meals will be served at lunchtime (1300 - 1400 h).

The research assistants will be responsible for instructing and overview the kitchen helpers, supervising that the amounts and procedures described in the recipes are followed by the cooks, weigh the amounts of raw foods to be cooked in each dish, weigh the dishes and serve the test meals. Rice, vegetable curry and fish curry will be weighed and served separately to each child in disposable plastic containers. Disposable plastic containers will be used for hygienic purposes, ease of weighing separate portions as well as ease of administration. Drinking water will be given *ad libitum*. The containers will be marked with the child's identification number. Leftovers of each dish will be weighed to calculate total intake.

We shall have 3 floors of a building to accommodate 3 groups of children.

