For the nutrient analyses of dishes, duplicate samples will be collected in labelled plastic boxes and stored frozen. One sample each of cooked rice (n=5) and vegetable curry (n=5) will be taken biweekly. For the three fish dishes, one sample each will be taken every week (n=9), in total 27. The duplicate samples will be used for chemical analyses of dry matter, vitamin A, energy, protein, fat, iron, calcium and zinc.

In order to motivate the children to comply with the study procedure, each child will be given a notebook, a pen and an identification card that can be hung around his/her neck. The identification card will be colour coded (each intervention group having a different colour) and include the child's name, ID number, parents' names, camp name, dates of study and the child's picture.

The research assistants will record all data collected daily with respect to attendance of the children, leftover dishes and duplicate samples and enter them in a computer programme.

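### The endpoint form on acceptance of mola is worded for children fed mola daily and makes no provision for mothers of mola children who left early

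*Protocol*

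**What the plan says.** Under Specific objectives, the fourth objective is to study qualitatively the mothers' perceptions of the supplementation "as well as the acceptance of mola for habitual use among the children and their families".

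The section on mothers' perceptions in the Methods sets the instrument. At endpoint a questionnaire "will be conducted (in the mola fish group) to evaluate the effect of the mola supplementation on the general well being of the children". Its second stated purpose is to gauge whether children and families would take up the mola meal as a regular food. The same section calls these data important for putting the results into practice on a large scale. It adds a second source: "A focus group discussion with 15 mothers at 3-4 sessions will be conducted to assess the perception".

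The questionnaire is Appendix 7. Its introduction states as a fact for every respondent: "Your child was given the mola curry every day during the study". Item 8 then asks whether the child liked eating the curry on each day of the study. Items 8B, 12C and 17B record why the child disliked it or why the mother would not go on giving it. There is no field for attendance, date of leaving or reason for leaving.

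Under Test meal preparation and distribution, two relevant records are kept for every child in all three arms: "Leftovers of each dish will be weighed to calculate total intake", and "The research assistants will record all data collected daily with respect to attendance of the children, leftover dishes and duplicate samples". Their uses elsewhere are nutrient intake (Food intake) and a compliance rule of 80% of the assigned meal eaten (Compliance). Neither is tied to acceptance.

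Under Calculation of sample size, the group size is raised from 37 to about 60: "Assuming a maximum possible drop out of 40" per cent.

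**The concern.** A child who stops coming because he or she dislikes the mola curry is strong evidence against acceptance. An interview held once, at endpoint, will reach that child's mother only if somebody seeks her out, and the protocol does not say that anyone will. If she is reached, the opening sentence and item 8 do not describe what happened to her child, and the form cannot record why the child left.

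Followed as written, the plan therefore describes acceptance mainly among families who stayed. If leaving is related to dislike of mola, the error runs in mola's favour, in results the protocol intends to use for implementation. Refusal is plausible: under Preliminary Observations, pilot children needed motivation to eat the meals, at least at first, although they also said that the dishes were very tasty. An analysis plan could tabulate attendance and leftovers later, but it could not recover interviews that were never held.

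**Working it through.** **Step 1: reproduce the planning figures** (Calculation of sample size). Inputs: Z values 1.96 and 1.28, SD of change 0.20 µmol/L in both groups, difference 0.15 µmol/L.

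- n = (1.96 + 1.28)² × (0.20² + 0.20²) / 0.15² = 37.3 per group; the protocol states 37.
- Allowing for loss: 37 / (1 − 0.40) = 61.7; the protocol states approximately 60.

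Both reproduce closely. The 40% is therefore a loss from any cause, applied equally to each arm, and set as a maximum.

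**Step 2: how many mola mothers could be missed.** The Compliance section gives two lower figures: at least 80% expected to come to feeding, and nearly 90% follow-up in previous studies. Reading these as losses of 20% and 10% is an interpretation, since the first concerns attendance rather than drop-out.

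| Loss | Mola children who left, of 60 | Remaining |
|---|---|---|
| 10% | 6 | 54 |
| 20% | 12 | 48 |
| 40% (planning maximum) | 24 | 36 |

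**Step 3: what this could do to an acceptance figure.** Let d be the proportion who left and are not interviewed, S the acceptance among stayers and L the acceptance among leavers. Acceptance over all children allocated to mola is (1 − d)S + dL. Reporting S instead overstates it by S − [(1 − d)S + dL] = d(S − L).

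The documents give neither S nor L, so the size cannot be estimated. The formula shows what it depends on:

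- If leaving has nothing to do with acceptance, S = L and the overstatement is zero at any d.
- Each 10-point gap between S and L adds 1 point at d = 10%, 2 points at 20% and 4 points at 40%.
- Worst case for illustration only, assuming S = 90% and L = 0: acceptance over all 60 is 0.9 × 90% = 81% at 10% loss, 0.8 × 90% = 72% at 20%, and 0.6 × 90% = 54% at 40%.

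**Step 4: who the form does and does not reach.** For a child who stayed and disliked mola, item 8 can be answered no, with reasons in 8B; item 12 can be answered no, with reasons in 12C; and the child can say so in item 17, with reasons in 17B. That child is counted. For a child who left, the timing is endpoint, the introduction is wrong, item 8 does not fit, and there is no place for the reason. The focus groups are not stated to include such mothers. The gap is this second group only.

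**The case against.** The case against is substantial. The form says that mola was given, not that it was eaten, and it has coded answers for dislike. The questionnaire is accompanied by focus groups. The methods place the form in the mola group without restricting it to completers, so interviewing mothers of leavers is not ruled out. Appendix 7 is visibly a draft, with answer options left open for pretesting and the price in item 16 blank. The objective is qualitative, and no acceptance percentage is planned. Entry requires children who eat fish.

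All of this stands, and it limits the point. It does not remove it: not ruling out an interview is different from providing for one, and a draft form is the cheapest moment to correct its opening sentence.

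A reader might go further and infer four things that the documents do not support:

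- **That up to 40% of mola children refuse mola and go uncounted.** The 40% is an all-cause ceiling in every arm. The protocol gives no figure for refusal, and its Compliance section points to lower losses.
- **That the questionnaire is the only source on acceptance.** The focus groups are a second one.
- **That leftovers serve only to compute intake.** The amount eaten also defines compliance.
- **That share of curry eaten should become the acceptance measure.** The objective concerns habitual use by children and families: whether the household would give mola, how often, and at what price. Eating a free curry while helpers urge the child to finish it, with vegetables held back until then, does not answer that. The records can only complement the form.

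**Conclusion.** The point holds in a narrow form. The acceptance questionnaire is set at endpoint, is worded for a child given mola every day, and has no provision for mothers of mola children who left early. That is about 6 to 12 of 60 if losses run at 10% to 20%, and no more than 24 of 60 under the planning maximum. Any overstatement equals the proportion missed times the difference in acceptance between stayers and leavers. Its direction favours mola only if leavers accept mola less, which is an assumption, and its size cannot be derived from the documents. This is a minor improvement to a secondary, qualitative objective.

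**What to change.** In the Methods section on mothers' perceptions, state that the form is given to the mothers of all children allocated to mola, at drop-out or at endpoint, and that the reason for leaving is recorded.

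In Appendix 7, reword the introduction to say that the child was offered the mola curry. Adapt item 8 to ask about the days on which the child attended, and add fields for date of leaving and reason.

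Report attendance (out of 6 × 9 = 54 meals) and the share of served fish curry eaten on attended days, by arm, beside the form's answers. The two rui arms give a comparison that a mola-only form cannot. Present these as a complement to the habitual-use questions, not a replacement for them.

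The cost is small. The interview takes about 10 minutes (abstract summary for the ethics committee, item 6), and only the mothers of leavers are added: 6 to 12 at the lower losses, 24 at most. Staff already visit households biweekly, and attendance and leftovers are already recorded. One limit should be stated in the report: because helpers urge children to finish the fish, leftovers will understate dislike, although the instruction is the same in every arm.

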**Section A: Questions for the Mother**

First I will like to ask you a question about mola in general:

**7. What do you consider as the beneficial effects of eating mola?**

- a. Full of vitamins
- b. Full of vitamin A
- c. Good for/protect eyes
- d. Nutritious
- e. Good for health
- f. Good for growth
- g. Increases blood volume
- h. Tasty
- j. Others \_\_\_\_\_

List other options during pretesting: \_\_\_\_\_

---

## Perception of Mola Form

Study ID#

**8. Did your child like to eat the mola curry each day during the study?**

1 = Yes      2 = No

**8A. If yes, why:**

- a. Tasty
- b. Felt full
- c. Less sick
- d. Happier
- e. Got more energy
- f. Grow better
- g. Others \_\_\_\_\_

List other options during pretesting: \_\_\_\_\_

**8B. If no, why not:**

- a. Did not taste good
- b. Did not like to eat mola curry every day

List other options during pretesting: \_\_\_\_\_

---

**9. Do you think that the mola curry had a beneficial effect on your child's health?**

1 = Yes      2 = No      3 = Do not know

**10. If yes, how did the mola curry benefit your child's health?**

- a. Felt full
- b. Less sick
- c. Happier
- d. Got more energy
- e. Grow better
- f. Good for/protect eyes
- g. Nutritious
- i. Others \_\_\_\_\_

List other options during pretesting: \_\_\_\_\_

---

**11. Did the mola curry have a negative effect on your child's health?**

1 = Yes      2 = No

**11A. If yes, what are the reasons?**

List other options during pretesting: \_\_\_\_\_

---

**Perception of Mola Form**

Study ID# | | | |

**12. If we ask you to give mola regularly could you continue to give your child mola?**

1 = Yes                      2 = No

**12A. If yes, why:**

- a. Good for the child's health
- b. The child likes mola
- c. Tasty
- d. Contain vitamin and minerals
- f. Mola is cheap
- g. Others \_\_\_\_\_

List other options during pretesting: \_\_\_\_\_

---

**12B. If yes, how often could you continue:**

- a. Never
- b. Every day
- c. 1- 2 times per week
- d. 3 - 4 times per week
- e. 5 - 6 times per week
- f. 1-3 times per mo
- g. < 1 times per mo

List other options during pretesting: \_\_\_\_\_

---

**12C. If no, why:**

- a. Child does not like mola
- b. Not tasty
- c. Bones
- d. Some family members do not like
- e. Mola is costly
- f. Others

List other options during pretesting: \_\_\_\_\_

---

**12D. Who decide in the household what the child should eat?**

- a. Mother
- b. Father
- c. Child

List other options during pretesting: \_\_\_\_\_

---

**Perception of Mola Form**

Study ID#

**13. If we tell you that mola is good for your child's health how frequent do you wish to give mola to your child?**

- a. Never
- b. Every day
- c. 1- 2 times per week
- d. 3 - 4 times per week
- e. 5 - 6 times per week
- f. 1-3 times per mo
- g. < 1 times per mo

List other options during pretesting: \_\_\_\_\_

---

**14. If we tell you that mola must be eaten with the head and eyes to benefit your child's eyes (vision), growth, health and wellbeing, will you always prepare the mola with the head and eyes?**

1 = Yes                      2 = No

**14A. If No, why?**

List other options during pretesting: \_\_\_\_\_

---

**15. If we tell you that mola is good for your child's eyes (vision), growth, health and wellbeing, in which way will you prepare mola for your child?**

- a. With the head
- b. Without head
- c. Both with the head and without head
- d. Fried
- e. Boil
- f. Smashed

List other options during pretesting: \_\_\_\_\_

---

**16. The present price of mola in the market is xx taka per xxx per kilo. Will you buy mola for this price?**

1 = Yes                      2 = No

**Perception of Mola Form**

Study ID#

**16A. If yes, how often will you buy mola?**

- a. Never
- b. Every day
- c. 1- 2 times per week
- d. 3 - 4 times per week
- e. 5 - 6 times per week
- f. 1-3 times per mo
- g. < 1 times per mo

**16B. If yes, how high a price are you prepared to pay?**    taka/kg

**16C. If no, how low a price are you prepared to pay?**    taka/kg

**Section B: Questions to the Child**

**17. Did you enjoy eating the mola curry?**

1 = Yes                      2 = No

**17A. If yes, why?**

List other options during pretesting: \_\_\_\_\_

---

**17B. If no, why not?**

List other options during pretesting: \_\_\_\_\_

---

**18. Did the mola curry make you feel different?**

1 = Yes                      2 = No

**18A. If yes, how?**

List other options during pretesting: \_\_\_\_\_

---

**18B. If no, why not?**

List other options during the pretesting: \_\_\_\_\_

---

Date..... Signature of interviewer.....

Code

# Appendix 8

International Centre for Diarrhoeal Disease Research  
[name]  
Dhaka-1000, Bangladesh  
Att. [name]

[figure not shown]
J.nr. 834/171-9  
[name]  
[contact]  
February 2. 2001

## B. Background

The Royal Veterinary and Agricultural University, Denmark (KVL) and the International Centre for Diarrhoeal Disease Research, Bangladesh (the Centre) share common interests of expanding scientific research and promoting educational exchange through a collaboration in the areas of nutrition and food sciences. Researchers in the KVL Research Department of Human Nutrition have expressed an initial interest in working with Centre scientists on nutritional field studies to be conducted in Bangladesh. Other areas of collaboration are expected as an outgrowth of this initial research activity.

## C. KVL

The Royal Veterinary and Agricultural University, Denmark (KVL) is a university that specialises in veterinary medicine, agricultural sciences, horticulture and food sciences. KVL through its Research Department of Human Nutrition awards advance degrees in Food Science and Nutrition and conducts nutrition research through its Department of Human Nutrition. As a means of expanding opportunities for field research in Bangladesh for its advanced degree candidates, KVL seeks to conduct nutrition research in collaboration with the Centre.

